^a Hematology tests: Hemoglobin concentration, hematocrit, red blood cell count, neutrophils, total and differential white blood cell, thrombocyte (platelet) count.

Confidential Page 37 of 195

^b Only for patients that require weekly hematology monitoring per section 4.3.2. To be captured as an unscheduled visit in EDC/RAVE.

Table 2: Part B – Schedule of Events/Evaluations

TOZ-CL05 PART B: OPEN-LAI	BEL PHA	SE								
Study Period	Start of Part B	1							Safety Follow-Up	Unscheduled
Study Week a	24 (±7 d)	26 (±3 d)	30 (±3 d)	36 (±3 d)	48 (±7 d)	60 (±7 d)	76 (16 weeks) (±14 d)	Termination ^p	80 (±3 d)	
Assessments Study Visit	(V7)	V8	V9	V10	V11	V12	V13	B98	V14	B97
Recording of concomitant and anti-PD medications		X	X	X	X	X	X	X	X	X
BP ^b , pulse ^b		X	X	X	X	X	X	X	X	X ^c
Weight				X	X		X	X	X	
Physical and neurological examination	(p /			X	X	X	X	X	X	X ^c
12-lead ECG ^d	# 7	X	X	X	X	X	X	X	X	X ^c
UPDRS Parts I, II, III and IV (in on state) ^e	- for Visit 7 (Week 24	X	X	X	X	X	X	X ^p		
mMIDI ^f	Š		X	X	X	X	X	X	X	X ^c
C-SSRS	t 7 (X	X	X	X	X	X	X	X	X ^c
ESS ^g	/isi			X	X		X	X	X	
PDQ-39 ^g	or 1						X	X		
SCOPA-cog ^g	'				X		X	X		
Fall questionnaire	τA				X		X	X		
TSQM-9 ^g	Рап						X	X		
EQ-5D 5L ^g							X	X		
Healthcare Resource Utilization	able	X	X	X	X	X	X	X		
Recording of AEs	See Table 1: Part A	X	X	X	X	X	X	X	X	X
Laboratory tests: hematology ^h , chemistry ⁱ (including thyroid function ^j)	Se	X	X	X	X	X	X	X	X	X °
Urine pregnancy test, females of childbearing potential k		X	X	X	X	X	X	X	X	X °
Urinalysis ¹		X	X	X	X	X	X	X	X	X °
IMP dispensing and/or return ^m	X	X	X	X	X	X	X	X		X
Tozadenant blood sampling		X n	X n							X c
Pramipexole blood sampling (applicable patients only)		X °	Χ°	Χ°	Χ°	X °	X °	X °		X °
eCRF completion	X	X	X	X	X	X	X	X	X	X

Confidential Page 38 of 195

Table 2: Part B – Schedule of Events/Evaluations (continued)

TOZ-CL05 PART B: OPEN-LABEL PHASE

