AE, adverse event; BP, blood pressure; C-SSRS, Columbia-Suicide Severity Rating Scale; d, day(s); ECG, electrocardiogram; eCRF, electronic case report form; EQ-5D-5L, EuroQol 5D-5L Health Questionnaire; ESS, Epworth Sleepiness Scale; ET, Early Termination; IMP, investigational medicinal product; mMIDI, Modified Minnesota Impulse Disorders Interview; PD, Parkinson's disease; PDQ-39, Parkinson's Disease Quality of Life Questionnaire; SCOPA-cog, Scales for Outcomes in Parkinson's Disease - cognition; TSQM-9, Treatment Satisfaction Questionnaire for Medication; UPDRS, Unified Parkinson's Disease Rating Scale; V, Visit.

Part B - Footnotes:

- ^a Visit windows provided are in relation to Visit 7 (Week 24).
- b Obtain and record BP and pulse measurements after at least 5 minutes supine rest and again after standing for approximately 1 minute and 3 minutes.
- ^c Optional assessments that may be performed for evaluation of AEs at the investigator's discretion.
- Resting supine 12-lead ECGs will be collected after the patient has been in a supine position for a minimum of 5 minutes. ECGs should be collected at a time during visit when the patient is not experiencing dyskinesia that would interfere with an adequate recording.
- ^e UPDRS to be measured in ON state approximately 1 to 3 hours after patients have taken a scheduled dose of levodopa (preferably their morning dose of levodopa). Patients will be instructed to have already taken their normally scheduled dose of levodopa and their IMP before arriving at the study site in order to have their UPDRS Part III evaluated in the ON state. UPDRS in the ON state will be measured at a time representative of the ON state in that patient, not in the patient's "best" ON.
- f If patient has one or more positive modules on the mMIDI, their continued participation in the study should be discussed with the Medical Monitor.
- g To be collected during patient's ON state.
- h Hematology tests: Hemoglobin concentration, hematocrit, red blood cell count, total and differential white blood cell, thrombocyte (platelet) count.

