- ¹ Blood chemistry (including liver function) tests: Aspartate amino transferase (AST), alanine amino transferase, (ALT), gamma-glutamyl transpeptidase (GGT), alkaline phosphatase (ALP), lactate dehydrogenase (LDH), total bilirubin (conjugated and unconjugated), albumin, creatinine, urea/BUN, bicarbonate, uric acid, total protein, sodium, chloride, potassium, calcium, phosphate, glucose, cholesterol, creatine phosphokinase (CK).
- ^j TSH, free T_3 , and free T_4 .
- Document method of contraception at Screening and verify continuation of (or any change to) contraceptive method at each visit. For female of childbearing potential, perform a urine pregnancy test.
- Urinalysis: Specific gravity, pH, ketones, blood, protein, glucose. If urine dipstick is positive for leukocytes, protein, or erythrocytes, a microscopic evaluation and culture will be performed.
- Patients will be instructed to take the assigned dose of open-label tozadenant by mouth BID, in the morning and in the evening preferably at the same time each day. The evening dose should be approximately 12 hours after the morning dose. Patients will be instructed to take their morning and evening doses at least 1 hour before or 2 hours after a meal and to refrain from eating for at least 1 hour after dosing.
- PK blood samples for plasma tozadenant concentrations will be obtained for patients having a visit in the morning (before 10:00 AM) who, as instructed, have not yet taken their morning IMP dose on the day of the visit. (No PK sample will be taken for patients who have taken their morning IMP dose before the visit.)
- Only for patients concomitantly taking pramipexole: During Part B, in the event of AEs thought to be pramipexole-related (e.g., dyskinesia, hallucinations, delusions, hypotension, somnolence, nausea, vomiting), either noted at the time of a scheduled study visit or an Unscheduled Visit: If a PK blood sample is collected for tozadenant it will also be analyzed for plasma pramipexole; if a tozadenant sample is not being collected, a PK sample for plasma pramipexole concentration will be collected. See Section 8.2.

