6.2.19 Visit 8 (Week 26)

Note: Confirm the arrangement for laboratory sample pick-up on the day of the Week 26 Visit with the courier (see Central Laboratory Procedures Manual).

- 1. A sample for plasma tozadenant concentration will be collected from patients who have refrained from taking their morning IMP dose prior to the visit, as instructed at the prior visit.
 - a. Record patient-reported date and approximate time of the previous (evening) dose of IMP.
 - b. Collect blood sample for plasma tozadenant concentration (before 10 AM). Record the date and time of PK sample collection.
 - c. Have the patient take their morning dose of IMP and record the date and time of the morning dosing in the clinic.
 - d. If the patient has an AE considered to be related to pramipexole, indicate the PK blood sample collected for tozadenant is also to be analyzed for plasma pramipexole. Record the patient-reported date and approximate time when the patient took the previous dose of pramipexole prior to sampling. (See Section 8.2.)

Note: For collection, processing, labeling and shipping of samples, follow the instructions provided in the Central Laboratory Procedures Manual.

- 2. Obtain samples for the following laboratory tests, and record the date and time of collection:
 - a. Hematology and chemistry (including liver function tests).
 - b. TSH, free T3, and free T4.
 - c. Urine sample for urinalysis.
 - d. Verify method of contraception has not changed since the previous visit. For females of childbearing potential: urine pregnancy test.

- 3. Assess AEs by asking open-ended queries and record the assessments.
- 4. Record concomitant medication use; assess and record any changes to anti-PD medication dose or regimen.
- 5. Obtain and record BP and pulse measurements after at least 5 minutes supine rest and again after standing for approximately 1 and 3 minutes.
- 6. Obtain 12-lead ECG and ensure the ECG is collected at a time when the patient is not experiencing dyskinesia that would interfere with an adequate recording. Assess any changes from Baseline, defined as the patient's baseline in Part A, for clinical significance.
- 7. Record the date and approximate time of the most recent dose of levodopa taken prior to the UPDRS assessment.
- 8. Perform the following assessment in the ON state:

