7.2 Unified Parkinson's Disease Rating Scale (UPDRS)

The UPDRS is a scale that was developed as an effort to incorporate elements from existing scales to provide a comprehensive but efficient and flexible means to monitor PD-related disability and impairment (Fahn et al, 1987).

The scale itself has four components, largely derived from preexisting scales that were reviewed and modified by a consortium of movement disorders specialists (Part I, Mentation, Behavior and Mood; Part II, Activities of Daily Living; Part III, Motor Examination; Part IV, Complications of Therapy). One of the core advantages of the UPDRS is that it was developed as a compound scale to capture multiple aspects of PD. It assesses both motor disability (Part II: Activities of Daily Living) and motor impairment (Part III: Motor Examination). In addition, Part I addresses mental dysfunction and mood, and Part IV assesses treatment-related motor and non-motor complications. Of all available clinical scales for the assessment of Parkinsonian motor impairment and disability, the UPDRS is currently the most commonly used.

Only Sponsor's designee-accepted raters may administer the UPDRS subscales in accordance with the requirements for background, experience in a research setting and training as documented on the Certificate of Rater Approval.

Patients will be instructed to have already taken their normally scheduled dose of levodopa and their IMP prior to arriving at the study site in order to have their UPDRS Part III evaluated in the ON state (within approximately 1 to 3 hours after taking their levodopa dose). UPDRS in the ON state will be measured at a time representative of the ON state in that patient, not in "best" ON. UPDRS Part III in OFF will be not be evaluated.

An example of the scale is provided in **Appendix 15.1**.

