11.2.3 Pharmacokinetic Variables

- 1. Tozadenant concentrations and time point of IMP intake and blood sampling.
- 2. Tozadenant concentrations at Weeks 26 and 30 (Part B).
- 3. Pramipexole concentrations and time point of pramipexole intake and blood sampling (in applicable patients only) at Baseline, Week 2, and Week 24 (Part A), and in the event of AEs thought to be pramipexole-related (Parts A and B).

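### Table 2 footnote e and section 7.2 omit the Week 26 and Week 30 exception on the morning IMP dose, so a patient-visit handled by either gives no pre-dose tozadenant sample

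*Protocol*

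**What the plan says.** Two places give an unqualified instruction to take IMP before the visit.

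- Protocol Table 2, footnote e, attached to the UPDRS row: "Patients will be instructed to have already taken their normally scheduled dose of levodopa and their IMP before arriving at the study site". The row is marked at Weeks 26, 30, 36, 48, 60 and 76.
- Protocol section 7.2, which describes the UPDRS for the whole study: "Patients will be instructed to have already taken their normally scheduled dose of levodopa and their IMP prior to arriving at the study site".

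The other places treat Weeks 26 and 30 differently.

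- Table 2, footnote n, on the tozadenant sampling row, limits the sample to patients with a morning visit "who, as instructed, have not yet taken their morning IMP dose on the day of the visit". It adds: "No PK sample will be taken for patients who have taken their morning IMP dose before the visit".
- The synopsis (Overview of Study Procedures, Part B) and section 6.1 both exempt Weeks 26 and 30 from taking the morning dose at home.
- Section 6.2.18 (Week 24) has staff ask the patient to hold the morning dose for Week 26. Section 6.2.19 (Week 26) does so for Week 30, and section 6.2.20 (Week 28) adds a reminder.
- Section 6.2.19 opens with: "A sample for plasma tozadenant concentration will be collected from patients who have refrained from taking their morning IMP dose prior to the visit". The dose is then given in the clinic. Section 6.2.21 (Week 30) follows the same order.
- Section 8.1 sets the same condition for sampling, and section 11.2.3 lists the Week 26 and Week 30 tozadenant concentrations as a pharmacokinetic variable.

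**The concern.** One patient on one morning is covered by two opposite instructions, and they sit in the same schedule table. The choice between them decides whether a planned sample exists. The Week 26 and Week 30 samples are the only scheduled tozadenant samples in Part B; the only other entry in that row of Table 2 is the optional one for unscheduled visits. Section 8.1 provides one sample per visit and no make-up sample is described. If the morning dose has been taken, that visit's contribution to the variable is gone.

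The table is also where a site would look. The synopsis and section 6.1 both send the reader to the schedule tables for the timing of assessments.

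**Working it through.** No formula applies, because the point concerns instruction text. The check is to see which instruction reaches each visit, and what follows.

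**1. Does footnote e reach Weeks 26 and 30?** Yes. It is attached to the UPDRS row as a whole, both visits are marked in that row, and the footnote excludes none. Section 7.2 is likewise unqualified.

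**2. Can both instructions be followed?** No.

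| Source | Morning IMP at Weeks 26 and 30 | Tozadenant sample |
|---|---|---|
| Table 2 footnote e | taken before arrival | not addressed |
| Section 7.2 | taken before arrival | not addressed |
| Table 2 footnote n | not yet taken | cancelled if taken |
| Synopsis; section 6.1 | taken in the clinic | drawn before the dose |
| Sections 6.2.18, 6.2.19, 6.2.20 (advice for the coming visit) | patient asked to hold it | not applicable |
| Sections 6.2.19 and 6.2.21 (visit steps) | taken in the clinic after the draw | drawn before the dose |
| Section 8.1 | not yet taken | only then |

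**3. Is it an omission?** It reads as one. Section 6.1 carries a closely similar sentence on levodopa and IMP before arrival and adds the exception for the two visits. Footnote e and section 7.2 lack it.

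**4. What happens to a patient-visit handled by footnote e or 7.2?** Under footnote n and section 8.1 there is no sample at that visit.

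**5. Which visit is more exposed?** The pre-visit telephone calls in Part A (sections 6.2.4, 6.2.7, 6.2.11, 6.2.14 and 6.2.17) each remind the patient to take IMP that morning. Week 26 is the first visit to reverse this, and the visit procedures give one instruction to hold the dose for it (6.2.18). Week 30 has an instruction and a reminder (6.2.19, 6.2.20). On the text, Week 26 is the less protected of the two.

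**6. How many samples?** Only a ceiling can be formed. The synopsis and section 3.1.2 anticipate about 360 patients continuing into Part B. With one sample at each of two visits, 360 × 2 = 720. The true planned number is lower: sampling is limited to visits before 10 AM, and 360 makes no allowance for withdrawal before Week 26 or Week 30. The documents give no rate at which sites would act on footnote e or 7.2 in place of the other text, so the number lost cannot be estimated from them.

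**The case against.** The strongest reply is that this is editorial. Table 2 itself carries the exception, in a footnote attached to exactly the Week 26 and Week 30 sampling cells, so a reader of the whole table meets both notes. The exception is also stated wherever staff speak to the patient: at Week 24 for Week 26, and at Weeks 26 and 28 for Week 30. The UPDRS steps inside 6.2.19 and 6.2.21 mention levodopa timing only, and no Part B visit procedure tells staff to have the patient take IMP at home before either visit. Specific text would normally be read ahead of a general footnote. The data at risk are modest too: section 11.5.2 plans a descriptive analysis of concentrations, with population analysis reported separately, and the SAP covers Part A only.

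Most of this stands, and it limits the point to individual patient-visits. A reader might infer that following Table 2 would lose the Part B variable altogether. The documents do not support that: the table contradicts itself, and the repeated hold instructions make wholesale loss unlikely.

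A reader might also infer real damage to the Part B UPDRS results, since the interval from IMP to assessment would depend on the text a site follows. That effect is slight. UPDRS is timed to levodopa throughout, in-clinic dosing at these visits already makes IMP timing differ from later visits by design, and the Part B UPDRS endpoints are exploratory. The disease-modification analyses in section 11.4.6 use change to Week 76 and slopes over Weeks 36 to 76.

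The reply does not remove the contradiction. Repeating the exception elsewhere leaves the opposite instruction in force in two operative places.

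**Conclusion.** The plan is wrong as written, in a small way. Footnote e and section 7.2 contradict the held-dose requirement at Weeks 26 and 30, and a patient-visit handled by either gives no tozadenant sample for a declared Part B variable. The size cannot be stated beyond the ceiling of 720, which is not an estimate of loss; any percentage put on it would be a guess.

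The conclusion rests on reading footnote e as applying to every marked cell of its row, since it names no exception, and on there being no make-up sample, since none is described. Discretionary tozadenant samples at unscheduled visits and pramipexole samples for related adverse events do not depend on a held dose and are unaffected. So are the Part A efficacy and safety results, the power and the alpha. This is a minor correction, worth making because it is nearly free.

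**What to change.** Reconcile Table 2 footnote e and section 7.2 with the synopsis, Table 2 footnote n, sections 6.1, 6.2.18 to 6.2.21 and 8.1, so that one instruction on the morning IMP dose at Weeks 26 and 30 appears in every place. Which instruction that should be is for the sponsor to settle. The change can go into the next amendment or a site memo. It costs the wording of one footnote and one section if those two are brought into line with the rest, and it adds no procedure, visit or sample.

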1.0 BACKGROUND AND RATIONALE

1.1 Background

Parkinson's disease (PD) is a chronic, progressive, neurodegenerative movement disorder characterized clinically by resting tremor, rigidity, bradykinesia and gait disturbance with postural instability. Other features can include masked faces, micrographia, and non-motor features including hyposmia, autonomic dysfunction, mood disturbances, and cognitive dysfunction. Estimates of the incidence and prevalence of PD vary considerably among studies due to differences in study populations, case ascertainment and diagnostic criteria. However, it is recognized that the incidence and prevalence of PD increase with age; and it is estimated that 1–2% of the population aged over 65 years are affected (Von Campenhausen et al, 2005).

The characteristic pathological findings in the brains of patients with PD are loss of dopaminergic neurons of the substantia nigra pars compacta coupled with the presence of intracytoplasmic inclusions (Lewy bodies). It is now appreciated that neurodegeneration also involves the olfactory system, the cerebral hemispheres, the lower brain stem, the spinal cord, and the peripheral autonomic nervous system. Current therapy is primarily based on a dopamine "replacement" strategy using the dopamine precursor levodopa. Levodopa has revolutionized the therapy of PD, but chronic treatment is associated with the development of motor complications ("wearing-off" and dyskinesia) in the majority of patients. Other available pharmacologic treatments include dopamine agonists, monoamine oxidase type B (MAO-B) inhibitors, and catechol-*O*-methyl transferase (COMT) inhibitors. These have not been shown to be superior to levodopa, but have been shown to either delay the need for levodopa or reduce OFF time in levodopa-treated patients. Each of these agents is thought to act directly on the dopaminergic system. Each has shown benefit, but there remains a need for agents that can treat and prevent motor complications (Olanow et al, 2009).

Adenosine A2a receptor antagonists have emerged as a potentially attractive new class of drugs for the treatment of PD (Pinna, 2009). A2a receptors are highly localized in the basal ganglia, specifically within the indirect output pathway which is important in the control of voluntary movement. Alterations in firing patterns in these neurons are also thought to be involved in the development of motor complications induced by levodopa. A2a receptor antagonists modulate gamma-aminobutyric acid and glutamate release in the basal ganglia along with other key neurotransmitters that modulate motor activity. In both rodent and primate models of PD, A2a receptor antagonists have been shown to produce alterations in motor behavior when administered alone or in combination with dopaminergic drugs, suggesting that they might be effective in the symptomatic treatment of PD (Bibbiani et al, 2003; Yu et al, 2006; Jenner et al, 2009). Because of the potential of A2a antagonists to inhibit abnormal firing of overactive D2-bearing neurons in the indirect striato-nigral pathway, they have the potential to improve OFF time in patients with PD. A2a inhibition may also slow neurodegeneration (Schwarzschild et al, 2003).

2.0 OBJECTIVES AND ENDPOINTS

2.1 Objectives

2.1.1 Primary Efficacy Objective (Part A)

The primary efficacy objective of this study is to demonstrate the efficacy of the A2a receptor antagonist tozadenant in the treatment of levodopa-treated PD patients experiencing end-of-dose "wearing-off", based on the change from Baseline to Week 24 in the number of hours per day spent in the OFF state.

2.1.2 Key Secondary Efficacy Objectives (Part A)

The key secondary efficacy objectives of this study are:

- 1. To evaluate the effect of tozadenant on good ON time (defined as the sum of ON time without dyskinesia and ON time with non-troublesome dyskinesia).
- 2. To evaluate the effect of tozadenant on UPDRS Parts II (Activities of Daily Living [ADL] subscale) + III (motor subscale) total scores.

2.1.3 Other Secondary Efficacy Objectives (Part A)

Other secondary efficacy objectives of this study are:

- 1. To evaluate the effect of tozadenant on investigator global impressions of improvement (Clinical Global Impression of Improvement [CGI-I]).
- 2. To evaluate the effect of tozadenant on patient global impressions of improvement (Patient Global Impression of Improvement [PGI-I]).
- 3. To evaluate the effect of tozadenant on UPDRS Part III (motor subscale) scores in the ON state.
- 4. To evaluate the effect of tozadenant on investigator global impressions of severity of illness (Clinical Global Impression of Severity [CGI-S]).
- 5. To evaluate the effect of tozadenant on UPDRS Part II (ADL subscale) scores.
- 6. To evaluate the effect of tozadenant on the number of hours per day spent in the ON state (without dyskinesia, with non-troublesome dyskinesia, or with troublesome dyskinesia).
- 7. To evaluate the effect of tozadenant on the number of hours per day spent in the ON state without dyskinesia.

- 8. To evaluate the effect of tozadenant in the number of hours per day spent in the ON state with any dyskinesia (troublesome or non-troublesome).
- 9. To evaluate the effect of tozadenant in the number of hours per day spent in the ON state with non-troublesome dyskinesia.
- 10. To evaluate the effect of tozadenant on PD-related quality of life as measured by Parkinson's Disease Quality of Life Questionnaire (PDQ-39) (total score and individual domain scores).
- 11. To evaluate the effect of tozadenant on UPDRS Part IV.
- 12. To evaluate the effect of tozadenant on UPDRS Part I.

